### 3.4 Duration of the study

The study is expected to last approximately 12-24 months, depending on recruitment.

## **4 DATA ANALYSIS**

The primary outcome that will be assessed is the loss of parental productivity measured in hours of paid or unpaid work missed due to caring for a child in the post-operative recovery period in caregivers who received the education tool compared to those who did not. Secondary outcomes that will be assessed include: household income (dollar amount) lost due to indirect productivity losses, hours of sleep lost, hours of leisure time lost, number of times that medical assistance is sought in the post-operative period, and need for compensated or non-compensated help at home.

Bivariate analysis will be performed using 2 sample t-tests for dichotomous predictor variables, Fisher's exact test or one-way ANOVA for categorical predictor variables, and Pearson correlation for continuous predictors where appropriate. A p-value of < 0.05 will be deemed statistically significant.

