## **1 BACKGROUND AND STUDY RATIONALE**

### **1.1 Background**

Terminology regarding how to measure the patient and family experience when a child receives medical or surgical care varies and includes patient-reported outcome measures (PROMs), patient-reported experience measures, and patient satisfaction. Preoperative patient education and postoperative patient participation are key components of the multimodal enhanced recovery after surgery (ERAS) protocols, which are gaining force in elective surgical procedures and impact both surgical outcomes and patient-reported outcomes. However, ERAS protocols and standardized care pathways have rarely been adopted in pediatric populations, and there exists a paucity of high-quality literature examining outcomes associated with implementation of enhanced recovery programs (ERPs) in children. Pediatric ERAS implementation has been met with many hurdles, including accounting for physiological differences between adults and children, the divergence of specific disease incidences between adults and children, and bridging the knowledge from adult pathways to pediatric-specific diseases which have no adult analogs. Therefore, specific pediatric preoperative patient/family education and postoperative patient/family participation needs to be developed to achieve reliable pediatric ERAS protocols. Medical procedures are considered especially stressful for children and parents. From over 5 million children that undergo elective surgery in North America each year, almost 75% of them experience considerable anxiety. Child anxiety is associated with many problems beginning with less cooperation with the anesthetic procedure, higher needs for analgesic usage, post-operative pain, slower recovery, delays in hospital discharge, and changes in behavior during the post-operative period. Also, preoperative anxiety can affect children's future interactions with medical personnel representing a long-term consequence. A major risk factor for children's distress is parental anxiety, which is also linked to physical and mental health problems for parents themselves. Based on these findings, different interventions have been studied in an attempt to reduce the burden for families. Audiovisual interventions for parents whose children were undergoing elective surgery had positive effects on both parental and children's preoperative anxiety. However, there has been no study on interventions to reduce parental anxiety during a child's surgical emergency.

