
Moreover, there has been little research, both in adults and in children, on the applicability and effectiveness of these same ERAS protocols for patients undergoing emergency surgery. Many of the limitations in acute care surgery come from the unpredictability of the timing for surgery and the variability of preoperative care, making it difficult to standardize postoperative care and offer perioperative counseling.

Although there are high numbers of surgical procedures performed in children, the impact on caregivers and families is poorly described. In the context of transitioning to same-day or early post-operative discharges, parents are facing the responsibility of having to care for their child early in the recovery process. This can lead to significant indirect costs associated with loss in productivity at work and at home, and increase caregiver anxiety and caregiver demands. The

magnitude of these indirect costs and loss in productivity has never been measured in a pediatric surgical setting. In reference to the ERAS guidelines, specifically the pillar of preoperative counseling and education, our aim in this research study is to implement an education tool, developed in collaboration with the McGill University Health Center Patient Education Office, for patients and caregivers in both elective and emergency surgical contexts and report its impact on indirect costs and caregiver productivity during the post-operative period. We hypothesize that by providing consistent and accessible information to patients and caregivers we may minimize anxiety, maximize satisfaction, and mitigate caregiver productivity loss during the post-operative recovery period, specifically within 2 weeks of discharge from the hospital.

We aim to examine the impact of a patient education tool in both the emergency and elective surgical settings:

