## 2 OBJECTIVES, HYPOTHESIS AND STUDY QUESTIONS

### 2.1 Objectives

- Create education tools for patients and caregivers to educate them on the diagnosis, surgical management, and post-operative recovery process for acute appendicitis, umbilical hernias, and inguinal hernias.
- Test whether the education tool reduces parental anxiety and improves satisfaction with care during a child's surgical illness.
- Test whether the education tools impact caregiver productivity loss in the immediate post-operative period, specifically 10-14 days post-discharge.

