### 2.2 Hypothesis

We hypothesize that implementing an education tool for patients and caregivers will decrease parental anxiety, improve satisfaction, and mitigate productivity loss among caregivers after hospital discharge.

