### 2.3 Study Question

Does the implementation of an education tool for patients and caregivers decrease preoperative parental anxiety and caregiver productivity loss in the post-operative period in the realm of pediatric surgery?

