#### 1. Pilot Phase (2-3 weeks) – Validation of Questionnaire

- A convenience sample of 5 patients with acute appendicitis and their families will be selected during their routine postoperative visits to provide input on the questionnaire. The preliminary questionnaire is attached, and was developed by the authors based on the Amsterdam Preoperative Anxiety and Information Scale (APAIS), Productivity and Disease Questionnaire (PRODISQ), the Health and Labor Questionnaire (HLQ), and a literature review.
- A convenience sample of 5 surgeons and 5 nurses will also be solicited to provide feedback.
- The questionnaire will be adapted based on qualitative feedback from the participants listed above.

2. Pre-Implementation Phase (100 patient/approx. 6 months)

- All patients with acute appendicitis who undergo appendectomies will be eligible to participate, and families will be consented prior to surgery. The parental anxiety assessment will be done only before surgery with the Amsterdam Preoperative Anxiety and Information Scale (APAIS). In addition, the email of one of the primary caregivers will be collected, and the caregiver will receive an email with a link to the post-operative questionnaire 10 days post-discharge. At 14 days post-discharge, they will receive a reminder email with the link to the questionnaire. All responses to the questionnaire are voluntary and anonymous.

Before Surgery	Obtain Consent
	Amsterdam Preoperative Anxiety and Information Scale (APAIS)
	Collection of email of primary caregiver
10 days Post-operative	Link to Parental Productivity Survey will be sent
14 days Post-discharge	Reminder email with link to the questionnaire will be sent.

3. Post-Implementation Phase (100 patient/approx. 6 months)

- The education tool will be distributed to families whose child is undergoing an appendectomy. The parental anxiety assessment will be done in the same way as above, only before surgery with the Amsterdam Preoperative Anxiety and Information Scale (APAIS). In addition, the email of one of the primary caregivers will be collected, and the caregiver will receive an email with a link to the post-operative questionnaire 10 days post-discharge. At 14 days post-discharge, they will receive a reminder email with the link to the questionnaire. All responses to the questionnaire are voluntary and anonymous.

Before Surgery	Obtain Consent
	Amsterdam Preoperative Anxiety and Information Scale (APAIS)

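### Parental anxiety and satisfaction with care are effects to be tested, but Section 4 names neither as an outcome, and the protocol text describes no satisfaction measure for comparing the two phases

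*Combined protocol and SAP*

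**What the plan says.** The protocol states its aims several times. Section 1.1 expects that "we may minimize anxiety, maximize satisfaction, and mitigate caregiver productivity loss during the post-operative recovery period". Section 2.1 sets the objective: "Test whether the education tool reduces parental anxiety and improves satisfaction with care during a child's surgical illness". Section 2.2 hypothesises that the tool "will decrease parental anxiety, improve satisfaction, and mitigate productivity loss among caregivers after hospital discharge". Section 2.3 asks: "Does the implementation of an education tool for patients and caregivers decrease preoperative parental anxiety and caregiver productivity loss in the post-operative period"; it keeps anxiety and leaves satisfaction out.

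Section 4 makes hours of paid or unpaid work missed the primary outcome. It continues: "Secondary outcomes that will be assessed include: household income (dollar amount) lost due to indirect productivity losses, hours of sleep lost". The remaining secondary outcomes are leisure time lost, medical assistance sought after surgery, and help needed at home.

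Section 3 gives the APAIS before surgery in both phases and sends a productivity survey by e-mail after discharge in both. A second survey, on the education tool, appears in the post-implementation schedule only. On the content of the main survey, the pilot-phase text says "The preliminary questionnaire is attached" and gives its sources as the APAIS, two productivity instruments and a literature review. That attachment is not part of the text available for review.

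**The concern.** An effect that is hypothesised but not listed as an outcome has no declared place in the analysis. Its result can be given prominence or left out once the data are known. This matters for anxiety because Section 1.1 presents it as the evidence gap: "there has been no study on interventions to reduce parental anxiety during a child's surgical emergency".

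For satisfaction the risk is greater. In a before-after design the pre-implementation families are the only comparator. If they are not asked about satisfaction with care at the time, the question cannot be put to them later on equal terms. The interval since discharge would differ, and because Section 5.3 makes the answers anonymous and unlinked to e-mail addresses, a late answer could not be joined to the earlier response. The satisfaction objective would then go unanswered however many families were enrolled.

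**Working it through.** No arithmetic applies, and the plan gives no figure to reproduce on this point. The check sets the three effects hypothesised in Section 2.2 against the methods and the analysis section.

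| Effect (Section 2.2) | Also stated in | Measure described for both phases (Section 3) | Named outcome in Section 4 |
|---|---|---|---|
| Productivity loss | 1.1, 2.1, 2.3 | Yes: post-discharge survey | Yes: primary |
| Parental anxiety | 1.1, 2.1, 2.3 | Yes: APAIS before surgery | No |
| Satisfaction | 1.1, 2.1 | None described | No |

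*Count.* Section 4 names 1 primary + 5 secondary = 6 outcomes. Of the three hypothesised effects, one is among them and two are not.

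*Anxiety.* Most of a specification can be assembled from the text:
- The direction is in Section 2.1.
- The instrument and timing, the same in both phases, are in Section 3.
- The contrast, families with the tool against families without it, is in Section 4.
- Section 4 assigns a two-sample t-test to a two-level predictor, which phase is.

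Two things are absent: a statement that anxiety is an outcome, and the score to be analysed. The instrument's title covers both anxiety and information, so the score needs naming. The questionnaire was partly based on the APAIS and may settle this.

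*Satisfaction with care.* The protocol text gives no instrument, item, score or time point. The questionnaire sources named in Section 3 include no satisfaction scale. The education-tool survey has no pre-implementation counterpart, so it cannot support a between-phase comparison, whatever it asks.

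*Consequence.* If the attached questionnaire has a satisfaction-with-care item and goes to both phases, the comparison is possible and only the listing in Section 4 is missing. If it has none, the comparison cannot be made.

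**The case against.** There are five fair points on the other side.

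1. Section 4 introduces the secondary outcomes with a verb that need not close the list. That is so, and it makes the anxiety gap largely one of labelling. It does not remove the gap, because no other section gives either effect outcome status.

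2. The attached questionnaire may contain a satisfaction item. This stands in full. A reader might infer that satisfaction is not measured at all; the documents do not show that, only that the available text does not describe it.

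3. A reader might cite the data items in Section 3.3, none of which is satisfaction with care, as proof that it is not collected. That does not work. The same list omits the APAIS score, which Section 3 collects in both phases, so it is plainly incomplete.

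4. A reader might infer that the APAIS could be completed before the family receives the tool, which would leave the anxiety comparison uninformative. The documents do not support this as a defect. The post-implementation narrative mentions distribution of the tool first, and the schedule simply does not place the hand-over. The order is unstated, not shown to be wrong.

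5. Section 2.3 already omits satisfaction, and the primary outcome is untouched. Both are true. They limit the seriousness of the point and make withdrawing the aim an acceptable remedy, but Sections 2.1 and 2.2 still promise a test.

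**Conclusion.** The point holds and should be fixed. Two of three hypothesised effects are missing from the six outcomes named in Section 4.

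For anxiety the defect is modest: the data will exist in both phases, and what is lacking is outcome status and a named score. It would be wrong to say that anxiety cannot be analysed.

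For satisfaction with care the defect may be decisive for that objective. As described, the plan has no measure in either phase and so no between-phase comparison. This conclusion depends on the attached questionnaire having no such item, so confidence is moderate. If the item is absent, the loss becomes permanent for each procedure once its pre-implementation families have been surveyed.

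The primary productivity comparison is unaffected.

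**What to change.** 1. Check the attached questionnaire for a satisfaction-with-care item that families in both phases receive.
2. If there is one, name it in the protocol and list it in Section 4 as a secondary outcome. If there is none, either add one identical item to the day-10 survey in both phases, from the start of each pre-implementation phase, and list it as a secondary outcome, or remove satisfaction from Sections 2.1 and 2.2. The pilot already provides for adapting the questionnaire, so that is the natural moment to add it.
3. In Section 4, list the APAIS anxiety score as a secondary outcome, name the score, and compare it between phases with stratification by, or adjustment for, surgical procedure. Section 4 describes only bivariate tests, so this needs one added sentence on the method, and each APAIS form must carry the phase and procedure.
4. Optionally, state in the post-implementation schedule where tool hand-over falls relative to the APAIS. This is a clarification only. Fixing the order may be harder for appendectomy, since Section 1.1 notes that "Many of the limitations in acute care surgery come from the unpredictability of the timing for surgery".

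The cost is protocol wording, at most one survey item and ethics board review. It also brings one or two more secondary tests, so the secondary results should be labelled supportive. No extra families are needed and the primary outcome does not change.

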## 3 STUDY METHODS

This study is a collaboration between the Harvey E. Beardmore Division of Pediatric Surgery and the Patient Education Office, with whom we have developed a plain-language patient education tool for appendectomies.

This study has several phases, which will be similar for all three surgical procedures. For convenience, the phases have been described in relation to the first surgical procedure that will be examined, namely appendectomy:

This study has several phases:

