### 3.2 Period studied

We anticipate a period of enrollment of approximately 6 months for each surgical procedure, as specified above in Section 3. We will aim to have 100 patients for the Pre-Implementation Phase & 100 patients for the Post-Implementation Phase.

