### 3.3 Description of data being retrieved

For each patient, we plan to collect answers from the circulated questionnaires, which will include questions related to the child and caregiver. This survey will not collect any identifiable information. However, we will collect some patient/parent information including:

- Age of the child and caregiver
- Relation of the caregiver to the child
- Caregiver's education level
- Caregiver's yearly income
- Caregiver's work hours

To assess indirect resource use (productivity losses) we will collect the following information:

- Hours absence from paid or unpaid job
- Loss of leisure time and sleep
- Access to compensated or uncompensated help at home
- Number of follow ups with medical personnel during the child's recovery
- Utility of education tool

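### The tool and no-tool groups are consecutive, non-randomised phases, but the primary comparison is planned with unadjusted bivariate tests although relevant covariates are collected

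*Combined protocol and SAP*

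**What the plan says.** Section 2.3 asks a causal question: "Does the implementation of an education tool for patients and caregivers decrease preoperative parental anxiety and caregiver productivity loss".

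Section 3 sets exposure by phase. The first is the "Pre-Implementation Phase (100 patient/approx. 6 months"). A post-implementation phase of the same size and length follows, in which families are given the tool. Section 3.2 repeats the target: "We will aim to have 100 patients for the Pre-Implementation Phase & 100 patients for the Post-Implementation Phase". Section 3 adds: "This study has several phases, which will be similar for all three surgical procedures". Randomisation is described nowhere. The words consecutive and non-randomised are mine, but they follow from this structure.

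Section 4 is the whole analysis plan. The primary outcome is hours of work missed, compared "in caregivers who received the education tool compared to those who did not". The methods are: "Bivariate analysis will be performed using 2 sample t-tests for dichotomous predictor variables, Fisher's exact test or one-way ANOVA for categorical predictor variables". Predictors on a continuous scale are to be examined by Pearson's coefficient. The primary test is not named. For a two-level exposure and an outcome in hours, the listed method is the two-sample t-test.

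Section 3.3 says: "For each patient, we plan to collect answers from the circulated questionnaires, which will include questions related to the child and caregiver". It lists child and caregiver age, relation to the child, education, income and "Caregiver's work hours". The hours of absence are listed in the same section. No section uses these variables to adjust the comparison, and none qualifies the conclusion for the before/after design.

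**The concern.** In a before/after comparison, the two groups can differ for reasons other than the tool. Survey response is voluntary (sections 3 and 5.2), and second-phase families are sent an extra survey, so the mix of respondents could differ by phase. A caregiver's usual work hours plausibly limit how many paid hours can be missed. If one phase had more full-time workers among its respondents, hours missed would differ even with an inert tool, and the t-test would credit or blame the tool for it.

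Section 4 speaks of predictor variables in the plural, so the section 3.3 variables may each be tested against the outcome. Doing that one at a time does not adjust the tool contrast.

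The choice has to be made in advance. Covariates selected after the results are seen would be open to challenge. Section 5.3 also says answers cannot be traced back to families, so a missing variable cannot be recovered later.

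**Working it through.** **The plan's own figure.** There is none to reproduce. The documents give no SD, effect size or power calculation, and 100 per phase is only a target.

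**Inputs from the documents.** 100 per phase (section 3.2); significance at p < 0.05 (section 4; I assume two-sided).

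**Assumptions.** No tool effect; within-phase SD of hours missed set to 1; five covariate parameters jointly explaining a share R² of 0.1, 0.2 or 0.3 of the variance; a true between-phase shift of 0.2 or 0.4 SD in the covariate score.

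**Formulas.**
- Bias of the unadjusted difference: b = √R² × shift.
- Standard error: √(2/100) = 0.141.
- Rejection probability: 1 − Φ(1.96 − b/SE) + Φ(−1.96 − b/SE).

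**Ends of the range.**
- R² 0.1, shift 0.2: b = 0.316 × 0.2 = 0.063; b/SE = 0.45; rejection about 7%.
- R² 0.3, shift 0.4: b = 0.548 × 0.4 = 0.219; b/SE = 1.55; rejection about 34%.

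**Simulation** (6,000 runs per cell, robust standard errors in the adjusted model, 100 per phase):

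| Shift | R² | Bias (SD) | t-test rejects | Adjusted model rejects |
|---|---|---|---|---|
| 0.2 | 0.1 | 0.063 | 7.4% | 4.8% |
| 0.2 | 0.2 | 0.089 | 9.2% | 4.5% |
| 0.2 | 0.3 | 0.110 | 12.2% | 5.0% |
| 0.4 | 0.1 | 0.126 | 14.4% | 4.5% |
| 0.4 | 0.2 | 0.179 | 24.6% | 5.4% |
| 0.4 | 0.3 | 0.219 | 34.1% | 4.4% |

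With 50 responses per phase, the t-test rejects 6-19% and the adjusted model about 4-5%.

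**Smaller shifts.** For one covariate correlated 0.3 with the outcome and shifted by 0.1 SD, b = 0.03 and the t-test rejects 5.5%.

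**Limits of adjustment.**
- If the covariates are measured with reliability 0.5-0.7, the adjusted model rejects 5-12% at 100 per phase.
- With balanced covariates and an unmeasured period shift of 0.2 SD, the t-test rejects 29-30% and the adjusted model 30-36%. Adjustment does not cure this; it only tightens the interval around a biased estimate.

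**Precision.** The ratio of adjusted to unadjusted standard error with five parameters and balanced covariates is 0.86-0.98 at 100 per phase and 0.89-1.01 at 50, reaching about 1.02 at 50 with imbalance. With twelve parameters at 50 per phase it reaches 1.09.

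**The case against.** **Chance imbalance is not the problem.** A reader might infer that any phase difference in a covariate biases the test. It does not. At 100 per phase, a covariate score differs by more than 0.2 SD by chance about 16% of the time (SE 0.141), and the 5% error rate already covers that. Only a systematic shift inflates the error. Hospital and eligibility criteria are the same in both phases, and no section shows that such a shift will occur. This stands, and it limits the claim.

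**The 34% is a corner of an assumed grid.** A reader might take it as this study's false-positive rate. The documents give neither R² nor the shifts, so no such rate can be stated. At the mild end the figure is about 7%.

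**Regression does not reach the main weakness.** The main threat in this design is the period effect, and adjustment leaves it in place. This also stands. It is the reason for changing the wording of the conclusion as well as the model.

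**Work hours.** A reader might infer that the item records hours worked after surgery, so that adjusting for it would condition on the outcome. The layout of section 3.3 does not favour that: the item sits with age, education and income, apart from hours of absence. Usual hours is the natural reading. The questionnaire is not in the text available to me, so stating the reference period is a precaution, not the correction of an error.

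**The fix may not be wording alone.** Section 3.3 does not list the procedure, and answers are not linked to emails (section 5.3). A per-procedure or pooled model therefore needs a way to identify the procedure. This stands and is costed below.

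**Conclusion.** The concern holds in limited form. Exposure is set by phase, the question is causal, and the only planned analysis of the primary outcome is unadjusted although usable covariates are collected in the same questionnaires. A systematic phase difference in those covariates would be reported as a tool effect.

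Confidence is high for this gap in the text. It does not extend to the size of the bias: the 7-34% range rests wholly on assumed shifts and R², and the figure of about 5% after adjustment requires a correctly specified model and well-measured covariates. The documents do not show that the groups will differ, nor that adjustment would turn the comparison into a causal one. It should be fixed because the improvement is cheap and has to be prespecified to be credible. The design itself remains workable.

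**What to change.** 1. **Section 4, primary analysis.** Prespecify a regression of hours missed on phase, adjusted for a short list from section 3.3: caregiver's work hours, child age, relation, education and income, coded with few parameters. Linear regression with robust standard errors is one suitable choice. Keep the t-test as the unadjusted sensitivity analysis. State that work hours means usual hours before the operation, and state how missing covariate answers are handled.
2. **Procedure.** Say whether the analysis is per procedure or pooled with a procedure term. Identify the procedure through procedure-specific survey links or one added item.
3. **Conclusion.** Word it as an association between phase and hours missed, and say that unmeasured period effects remain.
4. **Optional.** Add perforated yes/no to the appendectomy questionnaire. Section 1.1.1 puts perforation at 25-30% of cases, with longer admission; section 3.1.1 enrols both kinds, and section 3.3 does not list it.

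**Cost.** No extra patients. Five parameters change the standard error by a factor of about 0.86-1.02 at 50-100 per phase. Fuller coding with twelve could raise it by about 9% at 50 per phase, so relation, education and income need to be collapsed or scored. If 10-20% of covariate answers are missing, a complete-case interval widens by 5-12% (1/√0.9 = 1.054; 1/√0.8 = 1.118), which favours imputation with complete cases as a sensitivity analysis. The procedure identifier may need an amendment and ethics board review. The perforation item would need both, because section 5.2 limits collection to data outlined in the protocol, plus a check against the anonymity promise in section 5.3.

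### Section 4 does not say whether the primary comparison is pooled over the three procedures or made in each, and plans only unadjusted tests at p < 0.05

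*Combined protocol and SAP*

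**What the plan says.** Section 4 defines the outcome once: "The primary outcome that will be assessed is the loss of parental productivity measured in hours of paid or unpaid work missed". It also words the contrast once, "in caregivers who received the education tool compared to those who did not", without mentioning procedure. For a two-group predictor the method is a t-test: "Bivariate analysis will be performed using 2 sample t-tests for dichotomous predictor variables". The decision rule is "A p-value of < 0.05 will be deemed statistically significant". There is no procedure term, no stratification and no multiplicity rule.

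Other sections point in different directions on the unit of analysis:

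- Section 2.3 frames the question broadly. It asks about preoperative anxiety and about "caregiver productivity loss in the post-operative period in the realm of pediatric surgery".
- Section 1.1 speaks of two settings: "We aim to examine the impact of a patient education tool in both the emergency and elective surgical settings".
- Section 3 organises the work by procedure: "This study has several phases, which will be similar for all three surgical procedures".
- Section 3.2 plans recruitment the same way: "We anticipate a period of enrollment of approximately 6 months for each surgical procedure". It then gives 100 patients before and 100 after implementation, without saying whether that is per procedure or overall.

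**The concern.** A single contrast in a study of three procedures can be analysed in several ways: one pooled test, one test per setting, or one test per procedure. Section 4 does not choose, so the choice could be made after the results are seen. Each route has its own weakness.

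- **Pooled.** The t-test mixes emergency appendectomy, including perforated cases with longer admissions (Sections 1.1.1 and 3.1.1), with elective hernia repair. The phases run one after the other without randomisation, and the questionnaire is voluntary. The procedure mix among respondents may therefore differ between phases.
- **Per procedure.** There are three primary tests, and no rule says how many must succeed before benefit is claimed.

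At stake is whether a reported p-value below 0.05 carries a 5% error rate, and whether the pooled difference reflects the tool or the case mix.

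**Working it through.** The documents give no family-wise error rate, power, effect size or SD, so there is no stated figure to reproduce. The inputs from the documents are the threshold of 0.05 (Section 4), three procedures (Section 3) and 100 + 100 patients (Section 3.2). Sidedness is not stated; two-sided is assumed.

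**1. Error rate by reading.** With k independent tests at 0.05 and any one counting, the chance of at least one false positive is 1 − 0.95^k. Independence is reasonable if each procedure has its own caregivers.

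| Reading | Calculation | Error rate |
|---|---|---|
| One pooled test | 1 − 0.95 | 5.0% |
| Emergency and elective | 1 − 0.95² | 9.75% |
| Three procedures | 1 − 0.95³ | 14.3% |
| Three procedures plus pooled | simulation, 2,000,000 draws, equal strata, normal statistics | about 16.1% |

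**2. Mix bias in a pooled test.** No means are given. Assume 28, 14 and 12 h for appendectomy, inguinal and umbilical repair, and no effect of the tool.

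- Balanced phase (100/100/100): (28 + 14 + 12)/3 = 18.00 h.
- Umbilical falls to 70 in the post phase only: (2800 + 1400 + 840)/270 = 18.67 h, a shift of +0.67 h.
- Inguinal falls to 70 instead: (2800 + 980 + 1200)/270 = 18.44 h, +0.44 h.
- Appendectomy falls to 70 instead: (1960 + 1400 + 1200)/270 = 16.89 h, −1.11 h.

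The value 70 is half the 140 umbilical repairs a year in Section 1.1.2. The shift is zero if the mix is the same in both phases or if the procedure means are equal.

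**3. Scale of that bias.** With an assumed within-procedure SD of 20 h, the SE for 300 versus 270 is 20 × √(1/300 + 1/270) = 1.68 h. The shifts are 0.67/1.68 = 0.40 SE and 1.11/1.68 = 0.66 SE.

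**4. SE inflation in a balanced pooled test.** The between-procedure variance is (10² + 4² + 6²)/3 = 50.7. The SE factor is √(1 + 50.7/SD²):

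- SD 10 h: √1.507 = 1.23
- SD 20 h: √1.127 = 1.06
- SD 40 h: √1.032 = 1.02

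**5. Detectable difference at 80% power, in SD units.**

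| 100 + 100 means | Pooled, 0.05 | Per procedure, 0.05 | Per procedure, 0.0167 |
|---|---|---|---|
| Per procedure (300 v 300 pooled) | 0.23 | 0.40 | 0.46 |
| In total (about 33 v 33 each) | 0.40 | 0.69 | 0.80 |

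**6. After the fix.** One prespecified test has a 5.0% error rate. Three tests at 0.05/3 = 0.0167 give 1 − (1 − 0.0167)³ = 4.9%.

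**The case against.** The strongest reply is that Section 4 names one primary outcome and words one contrast, so its natural reading is one pooled t-test at 5%. The 0.05 sentence is a general threshold. It is not a rule that any success wins. This stands. A reader might infer that the plan is to run three primary tests, each declared significant at 0.05, but no section says so. A reader might also join the 14% to the lack of stratification as one fault. They belong to different readings: a pooled test has no inflation, and separate tests cannot mix procedures.

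Second, three education tools for three diagnoses (Section 2.1) can be seen as three questions, for which adjustment across procedures is debatable. That is fair, and a single pooled test is not the only sound choice. The plan still has to say which choice it makes.

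Third, the pooled example is modest. The means and SD are assumed, and the umbilical shift works against the tool. This also stands, although a fall in appendectomy responses moves the result the other way. If recruitment meets 100 per procedure in each phase, enrolment is balanced by design and only differential response could change the mix. If 100 + 100 is the total, nothing in the plan holds the mix fixed.

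Fourth, one could extend the error calculation to all the secondary outcomes. That would assume independence between outcomes measured in the same caregivers, such as hours missed and income lost, and would treat labelled secondary outcomes as equal to the primary. It is not relied on here.

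**Conclusion.** The concern holds as a gap in specification with consequences on either reading. The primary comparison is not tied to one analysis, and the only method offered takes no account of procedure.

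- If pooled, the error rate is 5% apart from any mix bias. Under the assumed means and SD of 20 h, that bias is about 0.7 h in the umbilical example, and the SE is about 6% larger than it need be. Across the other assumptions tried, the shift runs from −1.1 to +0.7 h and the SE inflation from 2% to 23%.
- If tested in each procedure with any one counting, the family-wise error is about 14%. It is about 16% if a pooled test is also allowed, so 14% is not a ceiling.

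The documents do not show that inflation will occur, only that nothing prevents it. The point should be settled before analysis.

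**What to change.** In Section 4, prespecify one primary test at two-sided 0.05: the phase effect (post versus pre) on hours missed, over all procedures, in a linear model with procedure as a stratum term. Report the three procedure-specific effects with confidence intervals, and the phase-by-procedure interaction, as secondary.

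If the sponsor prefers three separate primary claims, say so and test each at 0.0167. Per procedure, this raises the detectable difference from 0.40 to 0.46 SD with 100 versus 100.

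Two further changes are needed:

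- Record the procedure with each anonymous response, by a survey item or a separate link per procedure. The data list in Section 3.3 does not include it, and under Section 5.3 answers cannot be traced back later.
- State in Section 3.2 whether 100 + 100 is per procedure or in total.

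The cost is a few sentences and one survey field or set of links. The downside is that the headline result becomes an average over procedures, so a benefit confined to one procedure would be only supportive evidence. The stratum term deals with procedure mix only; it does not remove other differences between sequential phases.
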